The spermatogenic cycle in humans lasts about 74 days (2.5 months) (5), which may be a vulnerable time for acute exposures such as drug intake. Large population-based studies addressing the associations between increased risk of adverse outcomes in the offspring following paternal exposure to drugs prior to conception are rare, as few databases offer the possibility of paternal-offspring linkage, and the effect of the paternal exposure may be very small. Thus far, only one study based on Danish national registers has reported an increased risk of ASD following paternal use of selective serotonin reuptake inhibitors (SSRIs) before conception (6), and concluded that the increased risk of ASD in the offspring associated with paternal SSRI use before conception may be attributable to paternal underlying psychiatric indications related to SSRI use or other unmeasured confounding factors. Other studies which evaluated the paternal exposure to Disease-Modifying Antirheumatic Drugs in Norwegian registries (7), or a large number of different prescription drugs in Norwegian registries including antiepileptic drugs (AEDs) (3,8), did not find an increased risk for adverse outcomes in offspring. Specifically, the risk of paternal exposure to valproate has thus far not been found to significantly affect offspring's outcomes (3,9).

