### 9.3.1 Exposure definition and measures

Within the AEDs, the primary exposure of interest is the dispensation of valproate. Brand names and generics of all forms of valproate salts will be considered (sodium valproate, valproic acid, valproate semisodium and valpromide) and summarized under the term “valproate”. Valproate will be identified using Anatomical Therapeutic Chemical (ATC) code N03AG01.

*Drug exposure of the offspring is based on the use of AEDs by the father during a risk window prior to conception. Since the spermatogenic cycle is approximately 2.5 months, the risk window considered here is three months prior to conception. Further details are presented in section 9.3.1.3*

As reported in section 9.7.3.2, in the primary analysis, paternal exposure to valproate (monotherapy) will be compared to paternal exposure to lamotrigine or levetiracetam (composite monotherapy). These drugs are generally associated with lower risk of teratogenicity for the offspring of women, however it is unknown whether the effect is the same in men. Lamotrigine and levetiracetam will be identified using ATC codes N03AX09 and N03AX14, respectively. Since polytherapy is indicated for medically refractory epilepsy (14), in order to avoid the risk of disease severity bias associated to polytherapy, evaluation of AED exposure according to monotherapy is preferred for comparative analyses. In this section, definitions of monotherapy and polytherapy are only discussed for AEDs. Co-medications (other than AEDs) are defined in section 9.3.3 (Potential confounding variables). Monotherapy is defined as the exposure to a single AED, whilst polytherapy is defined as any combination of AEDs (including valproate among the exposed and excluding valproate among the unexposed), simultaneously or in sequence, within the 3-months risk window. For example, switching to or switching from an AED other than valproate, lamotrigine or levetiracetam, will be considered as polytherapy, and the offspring of these fathers will be excluded from the comparative analyses. This is because a washout period is not possible in clinical practice since subjects may not be unexposed for seizure control. Including people who were exposed to more drugs of the same class, in the period of interest, could lead to uncertainty in defining which drug is associated with the outcome.

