### 9.7.5 Sensitivity analyses

The following sensitivity analysis will be conducted:

1. *Variation of exposure time window for primary outcome:* Examine the association between extended risk window of paternal valproate exposure (6 months) and NDD, including ASD, in the offspring to investigate if there is an effect of valproate exposure other than through the spermatogenic cycle.
2. *Outcome of interest restricted to ASD specifically (ignoring all other NDD diagnoses):* Investigate the risk of ASD in offspring paternally exposed to valproate (monotherapy), compared to lamotrigine or levetiracetam (composite monotherapy) treatment at the time of conception.
3. *Exclusion of offspring with a birth weight lower than 1000gr or born prior to 8th month of pregnancy, for primary outcome.* There are suggestions for evidence of association between preterm birth/low birth weight and NDD (47–49). If AEDs affect preterm birth and preterm birth affects NDD, this means that preterm birth could act as a mediator between AEDs and NDD. In the same way, if AEDs affect very low birth weight and very low birth weight affects NDD, this means that very low birth weight could act as a mediator between AEDs and NDD. Adjusting for a mediator introduces a bias, therefore this sensitivity analysis will be performed excluding extremely low birth weight, very preterm and extremely preterm newborns to explore the potential impact introduced by inclusion of this sub-population of offspring on the point estimate.
4. *Handling of missing diagnoses for CM outcome:* Since a lot of diagnoses/reasons for spontaneous abortions and stillbirth could be missing, due to under-reporting, a sensitivity analysis will be performed to investigate the risk of CM using a broader definition of the outcome. It will include all the ICD-10 codes of interest where available, as reported in section 9.3.2.2, for live births and spontaneous abortions/stillbirths as well as all spontaneous abortions/stillbirths without an ICD-10 code for the diagnosis/reason. The main advantage of this broader definition of the outcome would allow to include in the analysis under reported cases of CM, on the other hand missing diagnoses related to cases different from CM could be included.

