### 9.9.2 Study analysis limitations

- Restriction to monotherapy could lower the generalizability of the results due to differences in real life clinical practice. One study found that approximately half of the population become seizure free on their first drug (65), while others need to switch or add additional AEDs. The selection of the cohort for analysis for the primary objective based on paternal valproate or lamotrigine/levetiracetam monotherapy use could potentially result in a small population, and therefore could be underpowered if the sample size falls below that required to detect the desired HR of interest. In the present study, patients who are on AED polytherapy are excluded from the primary analysis. To understand the population of AED polytherapy users, descriptive analysis will be conducted as an exploratory objective. Moreover, during the 3 months prior to LMP2, a father can be exposed to more than one AED in a sequence of monotherapies, that is an exposure to multiple drugs in the period at study, a polytherapy. For this reason, switchers are considered being in AED polytherapy treatment, therefore excluded from the comparative analyses. However, the frequency of switchers will be described.
- It is expected that few offspring will be both paternally and maternally exposed to AEDs, however there will likely be some. Offspring who fall into this category will be excluded in the primary comparative analysis. However, the descriptive analyses of the overall cohort will inform on the understanding of the characteristics of these offspring.

- The exposure window that affects the outcomes of the study could be shorter than the complete 3 months spermatogenic cycle. If so, the methodology used to assess paternal exposure may be able to examine the effect of proximity to conception, in that only selected clusters of paternal exposure can be evaluated. However, this restriction could result in very small sample size. Therefore, the rates of NDD could be under-estimated and the HR estimates of NDD could be biased towards the null.
- It is known that the exposure of AEDs and other medications during breastfeeding is associated with the outcomes of interest. Failing to account for exposure during breastfeeding could lead residual confounding. Breastfeeding data is only available for Denmark and only after 2012.

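### Sensitivity analysis 1 cannot isolate an effect outside the spermatogenic cycle, because its 6-month window contains the 3-month window chosen to cover that cycle

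*Protocol*

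**What the plan says.** Protocol section 7.1 gives the length of the cycle: "The spermatogenic cycle in humans lasts about 74 days (2.5 months"). Section 9.3.1 derives the primary window from it: "Since the spermatogenic cycle is approximately 2.5 months, the risk window considered here is three months prior to conception".

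Sensitivity analysis 1 in section 9.7.5 then reads: "Examine the association between extended risk window of paternal valproate exposure (6 months) and NDD, including ASD, in the offspring", with the purpose "to investigate if there is an effect of valproate exposure other than through the spermatogenic cycle". It names no group exposed only in the earlier three months and no model term that separates the two periods.

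Three rules decide who counts as exposed or as a comparator:

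- Section 9.3.1 treats several antiepileptic drugs (AEDs) as polytherapy when they are taken "simultaneously or in sequence, within the 3-months risk window".
- Section 9.9.2 says that "switchers are considered being in AED polytherapy treatment, therefore excluded from the comparative analyses", and justifies this by exposure to several drugs in the period under study. Section 9.7.3 words the exclusion more narrowly: read literally, it covers switches that involve an AED other than the three study drugs.
- Footnote 10 counts dispensations from the 6 months before conception if their supply reaches into the last 3 months, with unused daily doses carried forward.

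**The concern.** The stated aim is about mechanism: does valproate act by some route other than the cycle just before conception? To answer that, one needs fathers whose exposure lies outside the last 3 months. The planned analysis lengthens the window and so keeps the fathers exposed in the last 3 months in the exposed group. If the primary HR is raised, the 6-month HR will tend to be raised too, and a reader could take that as support for a wider effect.

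The same fathers matter for the primary estimate. The reference group is lamotrigine or levetiracetam monotherapy within 3 months of LMP2 (first day of the last menstrual period plus two weeks), with no condition on earlier valproate. If earlier exposure does matter, which is the possibility that this analysis raises, former users in the reference group move the primary HR toward 1. In a safety study that is the direction of missing a harm.

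**Working it through.** **1. Nesting.** The cycle is 74 / 30.44 = 2.43 months. The primary window is months 0-3 before conception and so covers it. The sensitivity window is months 0-6. It contains both, and a father treated throughout is exposed under either definition.

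**2. Where the informative fathers go.** These took valproate in months 4-6 and not in months 0-3.

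- Stopped without replacement: they enter the 6-month exposed group and are pooled with continuous users.
- Moved to lamotrigine or levetiracetam: if the in-sequence rule carries over to 6 months, they become polytherapy and leave the analysis. Section 9.9.2 makes this likely. Section 9.3.1 ties the rule to 3 months and section 9.7.5 is silent. If the rule stays at 3 months, these fathers have no defined group.

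On no reading do they form a contrast of their own.

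**3. Rest of the plan.** The exposure clusters (section 9.3.1.3) and cumulative dose (sensitivity analysis 10) use only the 3-month window. The discordant-sibling analysis is descriptive.

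**4. Illustration of the nesting.** From section 9.5: HR 2.0, 4% reference risk, 589 per group required, 4,080 valproate-exposed offspring projected. The planned total of 1178 reproduces with Freedman's formula: (1.960 + 0.842)² × ((1+2)/(1−2))² = 70.64 events, and 70.64 / 0.06 = 1177.3.

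Assumed: a share f of the 6-month exposed group took valproate only in months 4-6, the reference group is unchanged, and group sizes are equal.

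- Effect only through the last 3 months: ratio = (1 − f) × 2 + f × 1 = 2 − f
- Same effect in months 4-6: ratio = 2.00

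The chance that the 6-month result differs significantly from 1 when the effect lies only inside the 3-month window is Φ(ln(2 − f)/SE − 1.96), with SE = √(1/(0.04n) + 1/(0.04n(2 − f))).

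| f | 6-month ratio, effect inside only | Chance significant, n = 589 | Chance significant, n = 4,080 |
|---|---|---|---|
| 2% | 1.98 | 0.77 | about 1.00 |
| 5% | 1.95 | 0.75 | about 1.00 |
| 10% | 1.90 | 0.71 | about 1.00 |
| 20% | 1.80 | 0.63 | about 1.00 |

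So with no effect at all outside the cycle, the 6-month analysis would usually be positive. The SE here tests one ratio against 1. It ignores weighting and clustering by father.

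**5. Reference group.** A father who moved from valproate to lamotrigine before the 3-month window, with no valproate supply carried into it, is a lamotrigine monotherapy comparator in the primary analysis. If supply is carried in, footnote 10 makes him polytherapy and he is excluded. The protocol gives no count of such fathers and no effect for earlier exposure, so only the direction of the bias can be stated.

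**The case against.** The heading of sensitivity analysis 1 speaks only of varying the time window. As a robustness check that is legitimate, and the primary estimate does not depend on it. A monotherapy rule for a sensitivity window is also commonly left to the statistical analysis plan. Both points stand, and they limit the defect to the stated aim and to the lack of a contrast that serves it.

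Four stronger readings are tempting and are not supported:

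- *That the analysis drops fathers who switched off valproate in months 4-6.* The protocol does not say so. It is a likely inference for those who moved to another AED and wrong for those who stopped without replacement.
- *That the 6-month result will reproduce the primary HR.* The ratio shifts with f, and the reference group changes too if switchers are excluded.
- *That carry-over in the comparators is never tested.* If switchers are excluded over 6 months, the reference group loses those who left valproate in months 4-6. Comparing the two HRs is then a partial check, though the protocol neither plans nor interprets it as one.
- *That the two mechanisms could not be told apart.* Setting the gap between 2 − f and 2.00 against the SE of one HR is the wrong yardstick, because the 3-month and 6-month estimates share most of their data. With the reference group fixed, the SD of their log difference is about q√(1/m₁ + 1/m₂), where m₁ and m₂ are the expected events in offspring of fathers exposed in the last 3 months and only in months 4-6, and q = m₂/(m₁ + m₂). Take 4,080 exposed, f = 5% and 8% risk in both: m₁ = 3,876 × 0.08 = 310.1 and m₂ = 204 × 0.08 = 16.3, so q = 0.05 and SD = 0.0127. The gap ln(2.00/1.95) = 0.0253 is then 2.0 SD. At 589 exposed it is about 0.8 SD.

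The last result supports the fix: what the data say about months 4-6 comes from the small added group, so it is better to examine that group directly.

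Footnote 10 also narrows the comparator point, because late switchers with leftover valproate supply are already out of the primary comparison.

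**Conclusion.** The concern holds for the aim. The nesting alone, without any assumption about switchers, means that a raised 6-month HR cannot be attributed to exposure outside the cycle. The 1.80 to 1.98 range illustrates this and rests on the assumed share f.

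The comparator point holds as a direction only: former valproate users without carried-over supply can sit in the primary reference group, and any effect of their earlier exposure would pull the primary HR toward 1. Whether this is negligible or material cannot be judged from the protocol. The matter is worth correcting, but it does not invalidate the primary analysis.

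**What to change.** 1. Add a disjoint contrast among fathers on lamotrigine or levetiracetam monotherapy in months 0-3: those with valproate supply in months 4-6 against those without.
2. Repeat the primary comparison with the reference group restricted to fathers with no valproate supply in the earlier months, as far back as extracted dispensing allows in each country.
3. Report counts and the HR with its confidence interval for both.
4. State how monotherapy is judged over 6 months, including where a valproate-to-comparator switch in months 4-6 is placed.
5. If the nested 6-month analysis is kept, restate its aim as robustness to window length.

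The cost is one re-derivation of exposure and some wording. Section 9.2.2 already requires 12 months of paternal enrolment before LMP2. How far back dispensing was extracted should be confirmed, since the Swedish inclusion criterion is framed on 192 days. The group in step 1 may be small and imprecise, and reasons for switching may confound it; the report should say both.

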### Milestones

- Study period allowing 24 months prior to index date: from January 1997 (Denmark), January 2010 (Norway) and 2007 (Sweden) to 31 December 2018 for Denmark and 31 December 2019 for Sweden and Norway.
- Registration in the EU PAS register: Q1 2020, after endorsement of protocol and before data extraction.
- Anticipated start of data extraction: Q4 2020

- End of data extraction: Q1 2021
- Progress report(s): Estimated Q1 2021 (12 months after PRAC endorsement)
- Interim report(s): Estimate Q3 2021 (Country-specific)
- Final report of study results: 23 January 2023, in accordance with PRAC
- Final report of study results v1.1, second submission: 27 March 2023
- Addendum to the final report of study results v1.1 (report on sensitivity analysis 2 and exploratory analysis 8): 27 March 2023
- Annex to the final report of study results v1.1 (compilation of sensitivity analysis tables): 27 March 2023
- Request for Amendment received from PRAC: 05 May-13 June 2023
- Partial Responses to List of PRAC Questions: 10 July 2023
- Submission of the deliverables related to results of the Norwegian re-run analyses: due 23 October 2023
- Submission of updated protocol v7: due 23 October 2023

*NB: Ethics and data request process in the countries of interest has been known to take more than 12 months in some cases. In anticipation of this, in the absence of data at the interim report due date(s), a progress report will be submitted. The final report submission date, therefore, will be driven largely by the date of data acquisition in each country of interest.*

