### 9.2.1 Study time period

The study time period will be based on availability of information from the National Registries; this will start from 01 January 2007 in Sweden, 01 January 2010 in Norway, and 01 January 1997 (01 April 2004 for secondary outcome) in Denmark in order to allow for 24 months average look back period for live births:

- pregnancy duration (9-months on average for live births),
- maternal and paternal preconceptional exposure (3-months),
- minimum look back period for confounders (12-months).

The study time period ends on 31 December 2018 for Denmark and 31 December 2019 for Sweden and Norway. The rationale for this choice is to include all data available from relevant

 In Denmark, for the period 1997-1 April 2004, stillborns born between 22nd and 28th weeks of gestation are not included in the Medical Birth Register but in the National Patient Register. However, since in the National Patient Register the linkage with the father is not available, the study period for the secondary outcome in Denmark is limited to 2004-2017 (or last available date).

linked registers, to capture a sufficient number of outcomes and exposures and linked family units, and to include the most up-to-date data available.

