**Table 4: Potential confounding variables by outcome**

Outcome	Father
NDD, including ASD	
 
• Age
 
• Bipolar Affective Disorder and mania (ever)
 
• Calendar year of conception of offspring
 

CM	
 
• Age
 
• Calendar year of conception of offspring
 

NDD: Neurodevelopmental disorders; ASD: Autism Spectrum Disorder; CM: Congenital Malformations

**Paternal age.** Multiple epidemiological studies suggest a relationship between advanced paternal age at conception, and adverse neurodevelopmental outcomes (19,20) and congenital malformations (21–23) in offspring. This has been particularly noted with regard to increased risk for autism. ‘Paternal Age’ will be considered a confounding variable a priori, for both outcomes.

**Paternal Bipolar Affective Disorder and Mania.** Valproate is indicated in the treatment of epilepsy, mania and migraine (24). Moreover, children of parents diagnosed with mood disorders including mania have been shown to present with increased risk of neurodevelopmental outcomes. For these reasons, in this study, paternal bipolar affective disorder and mania will be considered as potentially confounding the effect of paternal valproate use on the development of neurodevelopmental disorders in offspring.

**Maternal epilepsy.** There is an increased risk of NDD, including ASD, and CM, in the offspring of female patients with epilepsy (25,26). However the high risk of NDD, including ASD in the offspring of female patients with epilepsy may be due to foetal exposure to AED medication in utero (2), including valproic acid. Offspring from women with epilepsy will only be included in the descriptive analyses of the sample from source population following data extraction, and excluded from the comparative, sensitivity and exploratory objective analyses.

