5. *Simple pairwise comparison valproate vs lamotrigine and valproate vs levetiracetam in monotherapy.* Valproate, lamotrigine and levetiracetam are medications with similar indications but that may be systematically prescribed for different type of epilepsy (such as valproate for genetically determined epilepsy and lamotrigine for focal onset epilepsy) and potentially other indications (lamotrigine might be prescribed for bipolar disorder and levetiracetam is not). Moreover, they were licensed in different periods (levetiracetam since 2000; lamotrigine since early 1990s; and valproate since 1967 to

treat epilepsy and since 1995 to treat bipolar disorder) resulting in systematic different in the treated populations. With the objective to evaluate if there is a differential effect of using one or the other comparator, a supplementary analysis will be provided to contrast valproate paternal exposure to separately lamotrigine and levetiracetam paternal exposure for the purpose of both NDD and CM outcome:

- a. Describe the characteristics of mother, father and offspring for both the primary and secondary outcome cohort and separately for paternal monotherapy exposure to individual AEDs (valproate or lamotrigine or levetiracetam).
  - b. Investigate the risk of NDD, including ASD, in offspring paternally exposed to valproate (monotherapy), compared to lamotrigine (monotherapy) treatment at the time of conception.
  - c. Investigate the risk of NDD, including ASD, in offspring paternally exposed to valproate (monotherapy), compared to levetiracetam (monotherapy) treatment at the time of conception.
  - d. Investigate the risk of CM, in offspring paternally exposed to valproate (monotherapy), compared to lamotrigine (monotherapy) treatment at the time of conception, in Norway and Denmark only.
  - e. Investigate the risk of CM, in offspring paternally exposed to valproate (monotherapy), compared to levetiracetam (monotherapy) treatment at the time of conception, in Norway and Denmark only.

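### Sensitivity analysis 5c compares valproate with levetiracetam in Danish births from 1997, but by the protocol's own dates about a sixth of those births have no possible levetiracetam comparator

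*Protocol*

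**What the plan says.** Section 9.2.1 sets the start dates: "01 January 2010 in Norway, and 01 January 1997 (01 April 2004" for the Danish secondary outcome, with Sweden starting in 2007. On the end dates it says: "The study time period ends on 31 December 2018 for Denmark and 31 December 2019 for Sweden and Norway". Section 9.3.2.1 follows Danish children for NDD to age 12 at most.

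Section 9.3.1 defines exposure by the father's use before conception: "the risk window considered here is three months prior to conception".

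Section 9.7.5, item 5, sets out the pairwise comparisons. It gives different indications as one reason and the licensing history as another: "they were licensed in different periods (levetiracetam since 2000; lamotrigine since early 1990s", with valproate dated to 1967 for epilepsy. It accepts that this makes the treated populations systematically different. Item 5c then takes NDD under valproate "compared to levetiracetam (monotherapy) treatment at the time of conception". It carries no calendar limit. Items 5d and 5e, in the same list, do carry a limit by country.

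The provision for calendar time in the adjustment is Table 4, which lists "Calendar year of conception of offspring" as a potential confounder. Section 9.7.3.2.3 makes such variables candidates for the propensity score, uses inverse probability weights, and prefers weighting to matching partly so that patients are not lost. It states no restriction to the range where both treatments occur.

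**The concern.** A father whose child was conceived before 2000 could not, on the protocol's dates, have been on levetiracetam. In 5c the Danish valproate children from those years therefore sit in one arm with nobody opposite them. Their probability of being in the valproate arm is 1, so positivity fails. Inverse probability weights leave them in the analysis with a weight of about 1 and cannot create comparators for them. A spline or a regression term for year can only extend a fitted trend back into years without levetiracetam data.

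These children also have the longest possible follow-up, so they count for more in person-time than in number. If the rate of NDD diagnosis changed over birth years, that change enters the valproate arm only.

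Item 5 is meant to show whether the choice of comparator matters. Comparators exist throughout 1997-2018 for 5b (lamotrigine) but not for the first years of 5c. A difference between the two results may then partly reflect calendar time, or a real difference may be hidden.

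**Working it through.** **Inputs from the protocol.** Danish NDD births from 1 January 1997 to 31 December 2018, which is 22 birth years; follow-up to age 12 or end of 2018 (9.2.1, 9.3.2.1). Levetiracetam licensed since 2000, with no month given (9.7.5). Projected Danish valproate offspring about 1495 over 1995-2017, from 1.3 million births, 95% linkage, 1.2 per 1000 and 0.15% childhood exclusions; reference NDD risk 4% (9.5).

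**Assumptions.** Births uniform over time; no exit before age 12 or end of 2018; 266 days from conception to birth.

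**The plan's own figure.** 1,300,000 × 0.95 × 0.0012 × (1 − 0.0015) = 1480, against the stated 1495. It reproduces to about 1%. Over 23 years, 1495 / 23 = 65 valproate-exposed offspring a year.

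**Share of births.** Conception before 1 January 2000 means birth before about 23 September 2000, or 3 + 266/365.25 = 3.73 years after the start. 3.73 / 22 = 16.9%.

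**Share of follow-up.** Births in 1997-2006 give 10 × 12 = 120 person-years per unit of annual births. Births in 2007-2018 average 6 years each and give 12 × 6 = 72. The total is 192. The early births give 3.73 × 12 = 44.7 (unrounded 3.728), and 44.7 / 192 = 23.3%.

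**Range over the cut-off date**

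| Cut-off | Years | Births | Follow-up | Valproate offspring at 65 a year |
|---|---|---|---|---|
| Birth before 1 Jan 2000 | 3.00 | 13.6% | 18.7% | 195 |
| Conception before 1 Jan 2000 | 3.73 | 16.9% | 23.3% | 242 |
| Whole 3-month window after 1 Jan 2000 | 3.98 | 18.1% | 24.9% | 259 |
| Conception before 1 Jul 2000 | 4.23 | 19.2% | 26.4% | 275 |
| Conception before 31 Dec 2000 | 4.73 | 21.5% | 29.6% | 307 |

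If paternal valproate use fell over the period, the share among valproate offspring would be larger than the share of births.

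**Size of the bias.** The protocol gives no calendar trend in NDD diagnosis and no uptake curve for levetiracetam, so both are assumed. With a true HR of 1, levetiracetam use rising from 2000, and weights exact for each birth year, the weighted Cox HR was:

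- no trend: 1.00
- diagnosis rising 3% per birth year: about 0.95-0.96
- diagnosis rising 8% per birth year: about 0.89-0.91
- diagnosis falling 5% per birth year: about 1.10-1.12
- any of these trends, with births restricted to mid-2001 onward: 1.00

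Other uptake shapes moved these values by about 0.01-0.04.

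**Against the sampling error.** 65 × 22 × 4% = 57 expected valproate-arm events. The standard error of the log HR is at least √(1/57) = 0.13 from that arm alone. The largest downward bias above is ln(0.89) = −0.12, which is below one standard error.

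**The case against.** The strongest reply is that the protocol already sees the issue. It names the licensing dates, gives them as a reason for the pairwise analyses, lists calendar year as a confounder, describes characteristics by individual drug (5a) and by calendar period (9.7.2.1), and selects the propensity model on weighted balance. A rule on overlap could also sit in the statistical analysis plan, which is not to hand. This lowers the weight of the point but does not remove it. The protocol itself fixes the study period, the licensing date and the comparison, and these three do not fit together. Balance checks might show the gap but cannot close it. The remark in 9.7.3.2.1 that both groups are exposed over the same period concerns the three-month window, not calendar overlap.

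The reply is also right that the size rests on assumed trends, that item 5 does not state its own adjustment model, and that the bias is small beside the Danish standard error and far from the planned HR of 2.0.

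Three stronger readings are tempting, and the documents do not support them:

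- A reader might infer that the main comparison lacks a comparator in early Danish births. It does not: the reference group is lamotrigine or levetiracetam, and lamotrigine is dated to the early 1990s. Before 2000 that group is simply all lamotrigine. The same holds for 5b. Item 5e is untouched because the Danish CM period starts on 1 April 2004, and Sweden and Norway start in 2007 and 2010.
- A reader might infer that any gap between 5b and 5c would be purely a calendar effect. The protocol names epilepsy type and bipolar indication as other explanations.
- A reader might infer that every early child contributes 12 full years. Death, emigration and a first diagnosis end follow-up sooner.

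**Conclusion.** The point holds for one analysis: 5c, NDD, Denmark. The lack of overlap follows from the protocol's own dates and needs no assumption. Its extent, about 17% of births and 23% of follow-up, rests on uniform births and on where in 2000 licensing is placed.

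The direction and size of any bias are not known from the documents. An HR of roughly 0.89-0.96 under a true HR of 1 is what a rise in diagnosis of 3-8% per birth year would produce; a fall would push it above 1, and no trend would leave none. This will not by itself create or hide an effect of the planned size, but it weakens the reading of 5b against 5c. It is worth correcting, and it does not bear on the primary result.

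**What to change.** In section 9.7.5, item 5c, restrict Denmark to conceptions whose three-month exposure window falls after levetiracetam monotherapy is first dispensed to fathers in the Danish data. Repeat 5b for Denmark on the same restricted period and report it beside the full-period 5b, so that the two pairwise results cover the same years. Restrict in the same way any description under 5a that is read beside 5c.

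The cost is a date filter, a re-run of Danish 5c and one repeat of 5b. The early Danish valproate offspring drop out of 5c, where they have no comparator; they stay in the primary analysis and in the full-period 5b. Section 6 dates the final report to January 2023, so the re-run would follow known results and should be labelled as such. The Danish rule against releasing cells below five (9.9.1) still applies.
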